Difelikefalin's safety varies according to dose. Regarding safety, the majority of research revealed that adverse effects increased in frequency in a way that was dose dependent. Across all trials, nausea, vomiting, dizziness, diarrhea, and disturbances in gait were the most frequently reported adverse events (Enggalhardjo, et al., 2024). A dosage of 0.5 µg/kg of difelikefalin proved to have the most favorable benefit-risk profile, and it was safe to use up to 1.0 µg/kg (Narita et al., 2022).

Though difelikefalin appears to be a promising agent for the management of CKD-aP, evidence is still under-powered due to the paucity of the current data; therefore, more robust randomized controlled trials (RCTs) are required to confirm the benefit of difelikefalin (Saeed et al., 2024).

While recent clinical trials in Western populations have demonstrated its efficacy, data from low- and middle-income countries, such as Bangladesh, are scarce. The prevalence of CKD in Bangladesh surpasses the global and even South Asian averages. About 20 million people are suffering from chronic kidney disease, and of them, approximately 35,000–40,000 develop ESRD each year (Mostafi and Jabin 2023). This trial aims to evaluate the superiority of Difelikefalin over placebo in reducing pruritus severity among hemodialysis patients in a tertiary-level teaching hospital in Bangladesh.

2. Rationale

Pruritus in hemodialysis patients is a chronic and highly irritating condition associated with chronic kidney disease (CKD) that adversely affects sleep, mood, social participation and overall quality of life. The commonly used agents for CKD-associated pruritus often have limited efficacy or tolerability in many patients. Oral medications used to manage this condition are frequently associated with poor compliance due to a high pill burden. On the other hand, intravenous administration of difelikefalin after hemodialysis offers a practical and patient-friendly alternative. It uses the same dialysis access, avoiding the need for extra needle insertions. Previous studies have demonstrated that difelikefalin improves outcomes in patients with CKD-associated pruritus and enhances their quality of life. To my extensive search, data regarding the use of difelikefalin for CKD-associated pruritus in our population is scarce. This study aims to explore the effect of difelikefalin on CKD-associated pruritus in maintenance hemodialysis (MHD) patients in our population.

3.1. Research questions:

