- What is the effect of difelikefalin on CKD-associated pruritus in patients on maintenance hemodialysis?

3.2 Research hypothesis:

- Difelikefalin effectively reduces CKD–associated pruritus in maintenance hemodialysis patients.

4. Objectives

4.1 General objective:

- To evaluate the effect of difelikefalin in CKD-associated pruritus on maintenance hemodialysis patients.

4.2 Specific objectives:

- I. To determine the baseline scores of the WINRS scale and Skindex-10 scale in CKD-associated pruritus on maintenance hemodialysis patients..
- II. To estimate and compare the changes in the WINRS scale, and Skindex-10 Scale between the experimental and control groups.
- III. To assess the tolerability and detect any adverse effect of Difelikefalin in patients with CKD-associated pruritus on maintenance hemodialysis throughout the study period.

5. Materials and method:

5.1. Type of study: Randomized, placebo-controlled, double-blinded trial,

5.2 Place of Study: Department of Nephrology, Chittagong Medical College Hospital, Chattogram, Bangladesh.

5.3 Study period: One and half years from acceptance of protocol.

5.4 Study population: Adult CKD stage-5 patients on MHD in the dialysis unit of the Department of Nephrology, CMCH during the study period.

5.5 Study groups: Based on the interventions, there will be two groups in the study

I. Experimental group:

Standard symptomatic treatment for itching + Intravenous difelikefalin

II. Control group:

Standard symptomatic treatment for itching + Placebo

5.6 Sampling technique: Consecutive sampling. From the Selected participants, the intervention and control will be randomly assigned in a 1:1 ratio (block size of four) through computer-generated randomization.

5.7. Inclusion criteria:

- i. Adults aged ≥ 18 years.
- ii. Patient with chronic kidney disease on HD for ≥ 3 months.
- iii. Moderate-to-severe pruritus (WI-NRS score ≥ 4).
- iv. Able to communicate clearly with the Investigator .
- v. Willing and able to provide written informed consent prior to participating in this study.

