5.10. List of variables

Variables	Type	Value	Expression
Clinical			
Age	Discrete	In completed years	Mean±SD
Sex	Categorical	Male/Female	Frequency (%)
Duration of HD	Discrete	In completed years	Mean±SD
Duration of pruritus	Discrete	In completed months	Mean±SD
Cause of CKD	Categorical	GN/HTN/DM	Frequency (%)
Baseline use of antipruritic medication	Categorical	Absent/Present	Frequency (%)
WI-NRS score	Discrete	0-10	Mean±SD
Skindex-10 scale total score	Discrete	0-60	Mean±SD
Biochemical			
Calcium	Continuous	mmol/l	Mean±SD
Phosphate	Continuous	mmol/l	Mean±SD
PTH	Continuous	pg/ml	Mean±SD

Operational definitions:

- **Chronic Kidney Disease-Associated Pruritus:** CKD-aPis defined as severe and persistent itching directly related to kidney disease, without other underlying skin or systemic causes to explain the itching. (Hector alve..et al 2020)
- **MHD:** Maintenance haemodialysis was defined as regular haemodialysis treatment for at least 3 months for the management of ESKD.(Mambap, A.T., Che, I.A., Mahamat, M. *et al.* 2022)
- **Skindex-10:** The Skindex-10 scale was developed specifically for uremic pruritus and measures the weekly effect of itch across three domains (disease, mood and emotional distress, and social functioning) Scores on the Skindex-10 scale range from 0 to 60, with higher scores indicating worse itch-related quality of life. (Mathur et al., 2010).
- **Moderate-to-severe pruritus** will be defined as a mean score of >4 points on the 24-hour WI-NRS score calculated.Itching severity scores have been categorized in the literature as mild (<4), moderate (≥ 4 to <7), or severe (≥ 7) (Reich et al., 2012).
- **Efficacy outcomes:** The primary efficacy outcome will be the percentage of patients who will have an improvement (decrease) of at least 3 points from baseline at week 6 in the weekly mean score on the daily WI-NRS (Fishbane et al., 2020). The prespecified secondary efficacy outcomes will be the mean change from baseline at week 6 in the Skindex-10 scale total score (Fishbane et al., 2020).
- **Standard Symptomatic Treatment for Itching:** Standard Symptomatic treatment using antihistamin is useful. Gabapentin or Pregabalin UVB therapy ,oral charcoal or nalfuralfine might be the next line of therapy.(Mettang and kremer 2014)

5.11. Data collection instrument: A structured pretested case record form.

5.12. Data collection procedure:

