Baseline assessment: CKD patients in HD will be screened consecutively and prospectively by the above inclusion and exclusion criteria to select eligible patients. Eligible patients and their legal relatives will then fully explain the study protocol, their role in the study, and the risks of the study. They will be informed of their right to withdraw from the study at any stage. After getting written informed consent, they will be finally enrolled in the study. Detailed history clinical examination and relevant investigation will be done. Baseline demographic, clinical and biochemical information will be collected from the patients using the case record form and the scales. Blood samples will be collected after an overnight fasting period, with all aseptic precaution 5 mL of venous blood drawn into appropriate vacutainers. iPTH will be measured using a chemiluminescence immunoassay (CLIA). Serum calcium and phosphate will be analyzed using colorimetric methods on a Beckman Coulter AU480 or equivalent validated clinical chemistry analyzer.

Allocation: Once a participant is enrolled in the study and consents to participate, they will be assigned to a treatment group according to the randomization sequence. This assignment will be done immediately after the baseline assessment to ensure that it is truly random. Patients will be randomly assigned to either experimental group or placebo group with a 1:1 allocation. Randomization will be carried out using online software (Research Randomizer Version 4.0 at <https://www.randomizer.org>).

Blinding: The study will be conducted as a double-blind trial, meaning that both the participants and the investigators will be unaware of the treatment assignments.

Interventions:

In the experimental group:

Standard symptomatic treatment for itching + Difelikefalin Dose : 0.5 µg per kilogram of weight after each dialysis session.

Duration: 6 wks

In the control group:

Standard symptomatic treatment for itching + Placebo

Duration: 6 wks

Follow-up:

- i. At the end 3 wks by- WI-NRS scale, Skindex 10 scale & Adverse events
- ii. At the End of 6 wks: WI-NRS scale, Skindex 10 scale & Adverse events

During the 6-week intervention period, patients will report their worst itching intensity using the WI-NRS, and their quality of life will be assessed using the Skindex-10 questionnaire at prespecified follow-up intervals throughout the 6-week period.

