Safety will be evaluated by monitoring adverse events, vital signs, clinical laboratory measurements in both group.

5.13. Data analysis:

Data will be entered into an Excel sheet to generate the master sheet. After completion of data collection, master sheet will be fed into SPSS (Windows version 27.0) for analysis. This study has two types of data: Categorical and quantitative data. Kolmogorov–Smirnov (K-S) test will be used to determine the data distribution. Finding if there is a significant difference between the data, independent samples t-test (or Mann–Whitney test in case of non-parametric data) and Chi-square test for continuous and categorical data, respectively will be used. The difference between the repeated variable in distinct visits using repeated ANOVA with the change from baseline in the weekly mean WI-NRS scale, Skindex 10 Scale. The adjusted mean difference between the groups and its two-sided 95% CI will be presented. A p -value < 0.05 will be considered significance.

5.14. Expected outcomes: Difelikefalin will significantly reduce pruritus severity compared to placebo. Participants receiving difelikefalin will report improvements in quality of life and will exhibit a favorable safety profile, with no major adverse events.

5.15. The utilization of results: This trial will provide critical evidence on the effectiveness and safety of difelikefalin in a resource-limited setting, addressing a significant unmet need in the management of CKD-aP. If proven effective, difelikefalin could become a standard treatment option for CKDaP and improve the quality of life for hemodialysis patients in Bangladesh and similar populations globally. Efforts will also be made to present these results at conferences and publish them in peer-reviewed national and international journals. The results and observations of the study will be published as a thesis and submitted to the respective university as a part of the requirement for the MD (Nephrology) Phase B examination purpose. The results of the study will be presented to the Department of Nephrology, CMCH.

[figure not shown]

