Appendix
Case record form

Protocol Title: “Effect of Difelikefalin on CKD-Associated Pruritus in Patients on Maintenance Hemodialysis: A Randomized, Placebo-Controlled Trial”

Patient’s identification			
1	Patient ID No.		
2	Patient name :		
3	Adress		
4	Contact no:		
5	Study group	Experimental=1 Control=2	
Demographic characteristics			
1	Age:years	
2	Sex:	0=Female 1=Male	
Clinical characteristics			
1	Duration of HDMonths/years	
2	Duration of pruritusMonths/years	
3	Etiology of CKD	1=HTN 2=DM 3=GN 4=Others	
4	Baseline use of antipruritic medication	Anti histamin- Others-	
5	Online Kt/V		
Biochemical			
1	Calcium(mmol/l)		
2	Phosphate(mmol/l)		
3	PTH(pg/ml)		

	Follow-up data	Baseline	At 3-wk	At 6-wk
1	WI-NRS score			
2	Skindex-10 scale total score			

	Adverse Effect		3 weeks	6weeks
1	Nausea	N0= 0 Yes= 1		
2	Vomiting	N0= 0 Yes= 1		
3	Dizziness	N0= 0 Yes= 1		
4	Abdominal pain	N0= 0 Yes= 1		
5	Muscle spasm	N0= 0 Yes= 1		
6	Fall	N0= 0 Yes= 1		
7	Withdrawal	N0= 0 Yes= 1		
8	Expired	N0= 0 Yes= 1		
9	Others	N0= 0 Yes= 1		

	Complete the study per the Protocol 0= No 1= yes
	If not reason for drop-out 1. Adverse experience 2. Failure to return for follow-up 3. Patients refuse treatment 4. Patient died 5. Non-co-operation 6. Insufficient therapeutic response

Signature of the researcher:

Signature of the Guide/Co-guide

A. Worst Itching Intensity Numerical Rating Scale

INSTRUCTIONS

Please indicate the intensity of the **WORST ITCHING** you experienced over the past 24 hours by marking the box with the number that best describes it. After completing the scale below, please provide your initials in the **SUBJECT INITIALS** box indicating that you completed the scale by yourself and the **DATE** and **TIME** you completed the scale.

Worst Itching Over the Past 24 Hours

Please indicate the intensity of the **WORST ITCHING** you experienced over the past 24 hours.

0	1	2	3	4	5	6	7	8	9	10
										
NO ITCHING					WORST ITCHING IMAGINABLE					

B. Skindex-10 Scale

INSTRUCTIONS: During the past WEEK , how often have you been bothered by:							
	0 (Never bothered)	1	2	3	4	5	6 (Always bothered)

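### The safety statement in 5.12 promises vital signs and laboratory measurements that the follow-up schedule and case record form do not collect, and the form lists only three of the five adverse events the protocol calls most frequent

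*Protocol*

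**What the plan says.** Specific objective III (section 4.2) is "To assess the tolerability and detect any adverse effect of Difelikefalin in patients with CKD-associated pruritus on maintenance hemodialysis throughout the study period". Section 5.12 says how this will be done: "Safety will be evaluated by monitoring adverse events, vital signs, clinical laboratory measurements in both group".

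The only data collection instrument named in section 5.11 is "A structured pretested case record form". For blood tests, section 5.12 places collection at the start: "Baseline demographic, clinical and biochemical information will be collected from the patients using the case record form and the scales". The later contacts are given as a short list, of which the last entry is "At the End of 6 wks: WI-NRS scale, Skindex 10 scale & Adverse events"; the week-3 entry has the same three items.

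On what to expect from the drug, the Introduction reports that across trials "nausea, vomiting, dizziness, diarrhea, and disturbances in gait were the most frequently reported adverse events".

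The case record form in the Appendix has:
- single entries for calcium, phosphate and PTH, without visit columns;
- a follow-up table with two rows (the WI-NRS score and the "Skindex-10 scale total score") at baseline, week 3 and week 6;
- an adverse-effect table of nine no/yes rows at weeks 3 and 6.

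The Data and Safety Monitoring Plan holds a separate per-patient event log with columns for onset, end, severity, relatedness, action, outcome and comment.

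**The concern.** What a trial can say about safety is limited by what its forms ask for. If vital signs and laboratory values are promised as part of the safety evaluation but have neither a visit nor a field, that part of the evaluation cannot be reported, and no later analysis plan can recover data that were never collected.

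The adverse-event rows raise a related problem. Events asked about by name tend to be reported more fully than events left to a residual category. Diarrhea and gait disturbance are singled out by the protocol itself as frequent with this drug, yet neither is asked about. Because the trial is double-blind, under-recording would be expected in both arms. It would not create a false difference, but it would lower the counts and shrink any absolute difference. Section 5.14 expects a favorable safety profile, and a low count for events nobody asked about would read as support for that expectation.

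**Working it through.** The protocol gives no figure to reproduce here. The check is an item-by-item comparison of its own sections.

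**Step 1. Stated safety components against the places where they could be recorded.**

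| Component (5.12) | Week 3 and week 6 list (5.12) | Case record form | Board log |
|---|---|---|---|
| Adverse events | Listed | Nine no/yes rows, weeks 3 and 6 | Yes |
| Vital signs | Not listed | No field at any time | No field |
| Laboratory measurements | Not listed | Calcium, phosphate, PTH: one entry each, no visit columns | No field |

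Components with a follow-up field on the form: 1 of 3. Follow-up fields for vital signs: 0. Follow-up fields for laboratory values: 0. The variable list in 5.10 does not fill the gap: it has no vital signs, and its only biochemical variables are the same three, which 5.12 collects at baseline.

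**Step 2. The five events named in the Introduction against the form's rows.** The nine rows are nausea, vomiting, dizziness, abdominal pain, muscle spasm, fall, withdrawal, expired and others.

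| Event | Own row on the form |
|---|---|
| Nausea | Yes |
| Vomiting | Yes |
| Dizziness | Yes |
| Diarrhea | No |
| Gait disturbance | No (*Fall* is a possible consequence, not the same event) |

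Events with a row: 3 of 5. Events without one: 5 − 3 = 2.

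**Step 3. Where the two missing events could go.** There are two routes. The first is *Others*, which as it appears in the document is a no/yes item with no line to name the event; a count from it would mix event types. The second is the board log, which can hold any event. However, the protocol does not say who completes that log, when, or whether it enters the master sheet analysed under 5.13.

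**Step 4. The row *Withdrawal*.** It sits among adverse effects. The same form separately asks whether the patient completed the study and, if not, why, and the board's subject-status table also has a withdrawn status and a reason. Leaving the study is therefore already covered, and the row may mean withdrawal symptoms. The label does not say.

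**The case against.** The strongest reply is that the protocol is not as empty on safety as the form alone suggests. The board log is an event log in the same document, with timing, severity and relatedness, and it can record diarrhea or gait disturbance with a comment. The form's *Others* row can flag them, and *Fall* overlaps in part with gait disturbance. The form was also read from PDF, so the printed *Others* row may leave space to write.

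Much of this stands, and it limits the point. A reader might infer that the two events cannot be recorded at all; the documents do not support that. A reader might also infer that the monitoring board could not complete its own table. That is not supported either: nothing says the table is filled from the form's yes/no grid. What is missing is a statement of how the two relate.

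Two further replies are fair. Calcium, phosphate and PTH are described as baseline measurements, and nothing identifies them as the safety tests, so their single entries are not in themselves a fault. The fault is that the safety statement does not say which tests it means or when they are done. Recording events at weeks 3 and 6 also agrees with the follow-up list, so that interval is no contradiction.

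None of these replies supplies a follow-up field for vital signs or laboratory values.

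**Conclusion.** The point holds as an internal contradiction. Section 5.12 promises three safety components, while its own follow-up list and the appended form provide for one of them after baseline. Vital signs have no field even at baseline. This part rests only on the text and needs no assumption beyond taking the form as the instrument, as 5.11 does.

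The adverse-event part is secondary. Two of the five events the protocol calls most frequent are not solicited and cannot be tabulated by type and arm from the form. This assumes that *Others* has no space to specify the event, as it appears in the document.

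The number of events that would be missed cannot be derived from the documents. A reader might reach for the upper confidence limit for zero events among the 51 patients planned per arm. That limit describes sampling uncertainty, not events left unrecorded, and the protocol sets no numerical safety threshold against which a few missed events could be judged.

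The defect weakens the answer to objective III. It does not touch the primary efficacy comparison. It should be corrected before the form is used.

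**What to change.** 1. Add diarrhea and gait disturbance as rows in the adverse-effect table, and add a line to specify the event under *Others*.
2. Reconcile the safety statement in 5.12 with the follow-up list and the form. Either add vital-sign fields and named laboratory fields at baseline, week 3 and week 6, or delete those words from 5.12.
3. Label *Withdrawal* as withdrawal symptoms if that is meant, since leaving the study is recorded elsewhere on the form.
4. State that the existing board event log is completed for each event, by whom, and that it feeds the master sheet used in 5.13.

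The cost is a revised form and a little more recording time. A laboratory cost arises only if follow-up tests are kept. The budget gives one laboratory total (156,480) without a breakdown by test or visit, so the documents do not show whether repeat tests are already funded.

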Degree	Institute	University/Board	Field	Year
M.B.B.S			Passed	

3. Field of study : Nephrology
4. Research experience : None
5. Percentage of time to be devoted to this project : 100%
6. Number of Scientific Publication : None

.....

Signature of the Student

PART-C

Summary

Background: Pruritus is a common and distressing symptom among hemodialysis patients with chronic kidney disease (CKD), significantly impacting their quality of life. Difelikefalin, a selective kappa-opioid receptor agonist, has shown promise in alleviating CKD associated pruritus (CKDaP). However, its efficacy and safety in the Bangladeshi population remain under-explored. **Objectives:** This study aims to evaluate the effect of Difelikefalin, compared to placebo, in reducing pruritus, improving quality of life in CKD patients on maintenance hemodialysis. **Materials and Methods:** A randomized, placebo-controlled trial, double-blinded, will be conducted in the Department of Nephrology of Chittagong Medical College Hospital, Chattogram, Bangladesh for one and half years. A total of one hundred two CKD patients on maintenance hemodialysis will be included in this study. Patient with moderate-to-severe pruritus (Worst Itching Intensity Numerical Rating Scale [WI-NRS] score ≥ 4) will be enrolled and randomly assigned in a 1:1 ratio to receive either Difelikefalin (0.5 mcg/kg) or a placebo intravenously after each hemodialysis for 6 weeks. The primary outcome measure will be the change in WI-NRS score from baseline to week 6. Secondary outcomes will be measured by Skindex 10 scale. Adverse events and safety measures will also be recorded. The primary analysis will follow either an intention-to-treat or a per-protocol approach and will be performed using SPSS version 27. **Discussion:** Data from previous studies indicate that Difelikefalin can reduce the severity of itching and improve the quality of life in CKD patients on maintenance hemodialysis. Clinical trials are needed to better understand the safety and efficacy of Difelikefalin in CKD patients in our population.

PART-D

1. Introduction:

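### Section 5.13 promises an adjusted mean difference, but names only covariate-free methods, lets a normality test choose the test, and states no week-6 contrast

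*Protocol*

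**What the plan says.** Section 5.13 (Data analysis) sets out this sequence:

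- A Kolmogorov-Smirnov (K-S) "test will be used to determine the data distribution".
- Groups are then compared by "independent samples t-test (or Mann–Whitney test in case of non-parametric data) and Chi-square test for continuous and categorical data", respectively.
- Visits are handled as follows: "The difference between the repeated variable in distinct visits using repeated ANOVA with the change from baseline in the weekly mean WI-NRS scale", and likewise for Skindex-10.
- Finally: "The adjusted mean difference between the groups and its two-sided 95% CI will be presented". No adjustment variable and no visit is named.

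The outcomes are tied to week 6. The Summary (Part C) says: "The primary outcome measure will be the change in WI-NRS score from baseline to week 6". The efficacy definitions in section 5.10 instead make the primary outcome the share of patients improving by "at least 3 points from baseline at week 6 in the weekly mean score on the daily WI-NRS", with a secondary outcome of "the mean change from baseline at week 6 in the Skindex-10 scale total score".

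Section 5.12 schedules one intermediate assessment ("At the end 3 wks by- WI-NRS scale, Skindex 10 scale & Adverse events") and one at the end of week 6. The case record form has one WI-NRS cell and one Skindex-10 cell for each of baseline, week 3 and week 6.

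**The concern.** Three features of section 5.13 do not fit together.

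1. An adjusted estimate is promised, but nothing in the list adjusts for anything.
2. The data choose the test. If the K-S result points to Mann-Whitney, the test compares ranks while the promised estimate is a difference in means. The p-value and the interval could then disagree, and nothing says which governs.
3. The time point of the treatment effect is left open. A repeated ANOVA on changes has two levels, week 3 and week 6, while the outcomes are at week 6 only.

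The same data could therefore yield a t-test, a Mann-Whitney or a repeated-ANOVA result for one outcome, with the choice made after the data are seen. The baseline scores, which are collected anyway, would also go unused as a covariate.

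**Working it through.** **Plan's own figure.** The only calculation in the protocol is the sample size in section 5.9: (64×36 + 29×71)/35² × (1.96 + 1.63)² = 4363/1225 × 12.89 = 45.9, so 46 per arm; 46 × 1.10 = 50.6, so 51. It reproduces. It sizes the responder comparison and does not depend on anything below.

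**1. What each named method yields**

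| Method in 5.13 | Covariate stated | Mean difference | Week-6 effect |
|---|---|---|---|
| t-test | no | yes, unadjusted | yes, if run on week-6 change |
| Mann-Whitney | no | no | rank comparison only |
| Chi-square | no | no (proportions) | yes, for responders |
| Repeated ANOVA on change | no | yes, unadjusted | only if a week-6 contrast is added |

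No row gives an adjusted mean difference at week 6.

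**2. Repeated-ANOVA group main effect.** With two post-baseline visits it equals (d3 + d6)/2, where d3 and d6 are the group differences in change at weeks 3 and 6. The protocol gives neither, so these are assumed values:

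- d3 = 0.75, d6 = 1.5: average 1.125, which is 25% below d6.
- d3 = d6 = 1.5: average 1.5, no discrepancy.
- d3 = 1.5, d6 = 1.0: average 1.25, which is 25% above d6.

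The discrepancy can go either way and vanishes when the effect is constant.

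**3. Precision gained by baseline adjustment.** Assumed: baseline SD 1.5, follow-up SD 2.3, correlation r = 0.4, 46 per arm, week-6 difference 1.5 points.

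- Variance of change: 1.5² + 2.3² − 2×0.4×1.5×2.3 = 2.25 + 5.29 − 2.76 = 4.78.
- Residual variance under ANCOVA: 5.29 × (1 − 0.16) = 4.44.
- Ratio 4.44/4.78 = 0.93, so 7% lower variance and a confidence interval about 4% narrower (√0.93 = 0.96).
- Approximate power, t-test on change: SE = √4.78 × √(2/46) = 0.456; 1.5/0.456 = 3.29; Φ(3.29 − 1.96) = 91%.
- Approximate power, ANCOVA: SE = √4.44 × √(2/46) = 0.440; 1.5/0.440 = 3.41; Φ(3.41 − 1.96) = 93%.

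Simulation under the same assumptions gave 90–92% for the t-test and 92–93% for ANCOVA. With equal baseline and follow-up variances the ratio is (1 + r)/2: 0.70 at r = 0.4 (30% lower), 0.75 at r = 0.5 and 0.85 at r = 0.7.

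**4. The normality gate.** How often it rejects depends on which WI-NRS variable is analysed. Simulated rejection rates for K-S with the Lilliefors correction (SDs and r as in step 3; assumed means 7 and 4.5; day-to-day SD 1.0):

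| Variable (change from baseline) | Sets of 51 | Sets of 102 |
|---|---|---|
| One integer score per visit | 74% | 99.9% |
| Mean of seven daily scores | 6% | 8% |
| Skindex-10 total, 0–60 (assumed SDs 10 and 11.8) | 6% | 11% |

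Repeat runs for the integer score gave 70–71% and 99–99.8%. K-S without the correction rejected in only 4% (sets of 51) and 26% (sets of 102). Section 5.13 does not say which version is meant.

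**The case against.** The strongest reply is that the t-test named in section 5.13, run on week-6 change, already estimates the week-6 effect without bias and with nearly the power of ANCOVA. Covariate lists and contrasts are, besides, ordinary content for a statistical analysis plan. The first part is right and limits the size of this point. The second is right for detail, but section 5.13 does more than stay silent: it promises an adjusted estimate beside methods stated without a covariate, and it fixes a data-driven choice of test. 'Adjusted' might be meant as a model-based marginal mean from the repeated ANOVA. Without a covariate and with complete data, however, that is just the raw mean, taken over both visits unless a contrast is named.

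Some stronger readings are tempting but are not supported:

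- *The plan promises a week-6 adjusted difference that its tests cannot deliver.* The sentence on the adjusted difference names no visit; week 6 comes from the outcome definitions. Only the adjustment is out of reach of the t-test.
- *The plan will report an effect 25% too small, with power of 78% instead of 93%.* This needs two things the protocol does not state: that the group main effect of the repeated ANOVA is the reported result, and that the week-3 effect is half the week-6 effect. Section 5.13 describes the ANOVA as a comparison of visits. With a constant effect, simulated power was 94.5% for the repeated ANOVA and 92.4% for ANCOVA.
- *The K-S test will almost always reject because the scores are discrete.* This holds for a single integer score per visit, as the case record form layout suggests, but not for the weekly means that sections 5.10 and 5.13 define.
- *The primary analysis is invalid.* Section 5.10 and the sample size make the primary outcome a responder rate, which the chi-square test fits. The Summary makes it continuous. Until the two are reconciled, this point bears on the primary analysis only under the Summary's definition; under section 5.10 it bears on Skindex-10 and any supporting analysis of WI-NRS change.

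**Conclusion.** The point holds. Section 5.13 is inconsistent with itself on adjustment, lets a pretest separate the hypothesis test from the estimate, and does not tie the repeated ANOVA to the visit at which the outcomes are defined. None of this depends on assumed numbers.

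The size does. Against a change-score t-test, baseline adjustment gains about 7% in variance under the unequal-SD assumptions and 30% with equal variances at correlation 0.4. The WI-NRS entry threshold of 4 or more narrows the baseline range, which makes equal variances less likely for that scale. The gate would reject in roughly 70–100% of sets of single integer scores and about 6% of sets of 51 weekly means. The group main effect of the repeated ANOVA departs from the week-6 effect by half the difference between the week-3 and week-6 effects.

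This should be corrected, chiefly so that one pre-specified estimate and its matching test exist. It does not undermine the design or the sample size.

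**What to change.** In section 5.13:

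- Delete the K-S step as a rule for choosing the test.
- For WI-NRS and Skindex-10 total, pre-specify ANCOVA of the week-6 score on arm and baseline score. The arm coefficient is the same whether the score or its change is the response, so the outcome stays a change from baseline. The alternative is a mixed model on weeks 3 and 6 with arm, visit, arm × visit, baseline and baseline × visit.
- State that the adjusted mean difference is the week-6 contrast from that model, with its two-sided 95% CI and p-value.
- Keep Mann-Whitney on week-6 change as a sensitivity analysis.
- Keep chi-square for the responder outcome; baseline-adjusted logistic regression is optional support.
- State whether the analysed WI-NRS is a weekly mean or a single score per visit, and align the case record form with that.

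The cost is wording. The SPSS version already named fits either model, baseline scores are already collected, and 51 per arm is unaffected. The change should be dated before treatment codes are broken.
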